6.7. Definition of LAM-002A Dose-Limiting Toxicity (DLT)

A DLT will be defined as an AE or abnormal laboratory value meeting the criteria in Table 4 and that is assessed as unrelated to disease, a comorbid condition, intercurrent illness, or concomitant medications). For the purposes of dose escalation and determination of the LAM-002A MTDs, DLTs that occur within the first cycle of treatment must be included in decisions regarding dose escalation. DLTs or other clinically significant toxicities that occur after Cycle 1 may also be considered when determining the RP2D.

Table 4: Criteria for Defining Dose-Limiting Toxicities (DLTs)

Toxicity	Criteria
Hematology	CTCAE Grade 4 neutropenia lasting ≥ 7 days
	CTCAE Grade 4 febrile neutropenia
	CTCAE Grade 3 thrombocytopenia with bleeding that requires transfusion therapy
	CTCAE Grade 4 thrombocytopenia
Toxicity	Criteria
Gastrointestinal	≥ CTCAE Grade 3 vomiting or nausea despite the use of optimal anti-emetic treatments
	≥ CTCAE Grade 3 diarrhea despite the use of optimal anti-diarrheal treatments
Renal	Serum creatinine > 3.0 x ULN
Hepatic	Total bilirubin ≥ CTCAE Grade 3
	Total bilirubin ≥ CTCAE Grade 2 and ALT or AST ≥ CTCAE Grade 2
	or,
	for subjects with liver metastases at baseline, total bilirubin \geq 2.0 x ULN and ALT or AST \geq CTCAE Grade 3

Version 9, 18 Feb 2020

Toxicity	Criteria	
Treatment interruption/delays	Inability to administer ≥28/56 (BID schedule) or ≥42/84 (TID schedule) or ≥12/24 (intermittent schedule) planned LAM-002A doses in a treatment cycle due to drug-related AEs	
	or	
	Failure to recover from LAM-002A-related toxicities to baseline within 14 days from the last dose of LAM-002A in a cycle	
Other adverse events not listed above	Non-hematologic toxicities of CTCAE ≥ Grade 3 except for the following. • Alopecia • CTCAE Grade 3 forigue for < 72 hours	
	• CTCAE Grade 3 fatigue for < 72 hours	
	 Asymptomatic Grade 3 elevations in biochemistry laboratory values that last for ≤ 7 days that are not deemed to be clinically relevant. This includes electrolyte abnormalities that respond to medical intervention. 	
	Any LAM-002A-related adverse event that, in the opinion of the investigator, requires a dose reduction or discontinuation of treatment.	

Abbreviations: ALT: Alanine aminotransferase; AST: Aspartate aminotransferase; CTCAE: Common terminology criteria for adverse events; DLT: Dose-limiting toxicity; ECG: Electrocardiogram; NHL: Non-Hodgkin lymphoma; ULN: Upper limit of normal

6.8. Treatment Guidelines

6.8.1. Tumor Lysis Syndrome Prophylaxis and Therapy

The risk for TLS must be considered based on established algorithms (Cairo 2010, MDACC 2013, Roberts 2016):

- Low-risk: Serum LDH \leq ULN, all measurable lymph nodes \leq 5 cm, and absolute lymphocyte count (ALC) \leq 25 \times 10⁹/L
- Intermediate risk: Serum LDH > 1 to \leq 2 × ULN, \geq 1 measurable lymph node with an LD of > 5 but < 10 cm, or ALC > 25 × 10⁹/L
- High risk: Serum LDH > 2 × ULN, \ge 1 measurable lymph node with a LD of \ge 10 cm, or both \ge 1 measurable lymph node with an LD of \ge 5 but < 10 cm and ALC \ge 25 × 10 9 /L

Subjects who are at intermediate or high risk of TLS must receive medical prophylaxis according to the following prophylaxis regimens or similar institutional regimens:

- Intermediate Risk of TLS: These subjects should receive allopurinol, 100 to 300 mg orally every 8 hours starting ≥ 24 to 48 hours before the initial administration of LAM-002A on Cycle 1-Day 1 of therapy; of note, the maximum daily allopurinol dose is 800 mg, doses ≤ 300 mg need not be divided (but may be insufficient for high-risk subjects), and doses should be reduced by ≥ 50% in subjects with renal insufficiency. In addition, subjects who develop hyperuricemia should receive rasburicase, 0.2 mg/kg.
- High Risk of TLS: These subjects should receive allopurinol, 100 to 300 mg orally every 8 hours starting ≥ 24 to 48 hours before the initial administration of LAM-002A on Cycle 1-Day 1 of therapy; of note, the maximum daily allopurinol dose is 800 mg, doses ≤ 300 mg need not be divided (but may be insufficient for high-risk subjects), and doses should

be reduced by $\geq 50\%$ in subjects with renal insufficiency. In addition, high-risk subjects should receive rasburicase, 0.2 mg/kg, administered 3 to 4 hours prior to the first dose of LAM-002A.

In addition, subjects who are at high risk of TLS should be considered for in-hospital monitoring during the first 24 to 48 hours of LAM-002A administration.

Subjects who develop TLS may experience hyperkalemia, hypocalcemia, hyperuricemia, hyperphosphatemia, cardiac dysrhythmias, and acute renal failure; thus, close monitoring of electrolytes is important after initial therapy.

Subjects with TLS should receive intravenous hydration, rapid reversal of hyperkalemia, antihyperuricemic agents, and appropriate cardiac and renal support, including dialysis as indicated. Upon recovery to baseline functioning and as medically appropriate, such subjects should continue with protocol therapy to maintain tumor control.

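### Section 6.8.1: the top of the printed allopurinol range (300 mg every 8 hours, 900 mg/day) lies above the 800 mg daily maximum in the same sentence; a minor inconsistency to reconcile in both risk bullets

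*Combined protocol and SAP*

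**What the plan says.** Section 6.8.1 of the protocol sorts subjects into low, intermediate and high risk of tumor lysis syndrome. Those at intermediate or high risk "must receive medical prophylaxis according to the following prophylaxis regimens or similar institutional regimens".

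The allopurinol instruction is the same in the two risk bullets:

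- Dose and interval: "These subjects should receive allopurinol, 100 to 300 mg orally every 8 hours starting" at least 24 to 48 hours before the first LAM-002A dose.
- Daily limit, later in the same sentence: "of note, the maximum daily allopurinol dose is 800 mg".
- Two further notes in that sentence: first, "doses ≤ 300 mg need not be divided (but may be insufficient for high-risk subjects"; second, that doses should "be reduced by ≥ 50% in subjects with renal insufficiency".

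The bullets differ only in their rasburicase instructions, which play no part in this point. The section does not say how the upper end of the dose range is meant to fit under the daily limit.

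**The concern.** A range per dose, an interval and a daily maximum are three figures of which any two constrain the third. Here the range and the interval together allow a daily total that the maximum forbids. A site that prescribes the upper end at every administration is within the printed range and over the printed limit at the same time. Neither the site nor a monitor could tell from the text alone whether that prescription complies with the protocol or departs from it.

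What is at stake is the clarity of a supportive-care instruction. Prophylaxis itself is required for both risk groups, and the same wording stands in both bullets, so neither offers a consistent version to fall back on.

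**Working it through.** **Inputs, all from Section 6.8.1 (same in both bullets)**

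- Dose per administration: 100 to 300 mg.
- Interval: 8 hours.
- Stated daily maximum: 800 mg.
- Renal reduction: at least 50%.

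**Step 1. Doses per day.** 24 h / 8 h = 3.

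**Step 2. Daily total implied by the range.** Daily total = dose × 3.

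| Equal dose every 8 h | Daily total | Over 800 mg? |
|---|---|---|
| 100 mg | 300 mg | no |
| 200 mg | 600 mg | no |
| 250 mg | 750 mg | no |
| 266.7 mg | 800 mg | no (equal) |
| 300 mg | 900 mg | yes |

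The stated 800 mg is therefore not the upper end of the stated range, which is 900 mg/day.

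**Step 3. Size of the excess.** 900 − 800 = 100 mg/day; 100 / 800 = 12.5%.

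**Step 4. Where the conflict starts.** 800 / 3 = 266.7 mg. Equal doses above this and up to 300 mg are inside the range but over the maximum. Equal doses at or below it satisfy both figures. Unequal doses can satisfy both while still using 300 mg: 300 + 300 + 200 = 800 mg/day.

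**Step 5. Effect of the renal reduction.** 900 × 0.5 = 450 mg/day. With a reduction of at least 50%, the top of the range is 450 mg/day or less, which is under 800 mg. The conflict is therefore confined to subjects without that reduction.

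The only assumption is a 24-hour day with every scheduled dose taken.

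**The case against.** The strongest reply is that the 800 mg note is a cap and the sentence should be read whole: choose a dose from the range, subject to the daily limit. Read that way, most of the range is usable as printed, and no bullet tells a site to give 300 mg at every administration. This largely stands. It means that a site need not breach the limit, and that the two figures disagree at one end of a permissive range only. What remains is that the sentence does not say the range gives way to the maximum; the reader has to multiply and infer it.

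It is also fair to say that the requirement is for prophylaxis and not for this particular regimen, since similar institutional regimens are accepted and the allopurinol wording is advisory. That lowers the practical exposure. It does not make the printed regimen consistent.

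Two stronger readings may tempt a reader, and the documents support neither.

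- *That the text steers high-risk subjects towards the non-compliant end.* The remark about insufficiency concerns doses of 300 mg or less that need not be divided. Its natural sense is a low daily total. Everything above 300 and up to 800 mg/day remains open, so the remark does not push anyone to 900 mg/day.
- *That the conflict is worse for subjects with raised creatinine, whom inclusion criterion 7d can admit.* The same sentence calls for a reduction of at least 50% in renal insufficiency, and Step 5 shows that the conflict does not arise where it is applied.

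**Conclusion.** The inconsistency is real but minor. In both risk bullets, equal doses above 266.7 mg every 8 hours lie inside the printed range and exceed the printed daily maximum, by up to 100 mg/day (12.5%). The arithmetic is exact and uses only current text.

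Its reach is limited: it concerns subjects given the protocol's own regimen, near the top of the range, without the renal reduction, and at a site that does not read the maximum as a cap. It is a supportive-care matter that enters no endpoint definition, sample size, error rate or analysis set. A reader might infer that the section as a whole cannot be followed, or that sites are being directed to exceed the limit. The documents do not support either inference, because most of the range satisfies both figures. Nothing here says which of the figures is clinically right.

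**What to change.** Reconcile the per-dose range, the interval and the daily maximum in both the intermediate-risk and the high-risk bullet of Section 6.8.1, so that no dose inside the range can exceed the stated limit. If the maximum is meant to govern the range, the sentence should say so outright. The sponsor's clinicians should decide which figure stands.

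The cost is one line of text in two bullets, which can go into the next protocol amendment. No statistical section needs to change.

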6.8.2. LAM-002A

6.8.2.1. Premedications

Subjects taking LAM-002A by continuous administration may be offered antiemetics and antidiarrheals as necessary to control gastrointestinal symptoms as described in Section 6.8.2.6.1. For subject who do develop such adverse effects, sites should consider providing study participants with antiemetics and antidiarrheals so that these supportive care medications are readily available in case gastrointestinal symptoms related to LAM-002A recur or persist.

Subjects taking LAM-002A by intermittent administration are required to receive prophylactic antiemetic supportive care as described in Section 6.8.2.6.2.

6.8.2.2. In-Clinic LAM-002A Administration

For subjects receiving the continuous LAM-002A regimen, the morning dose of LAM-002A should be orally administered on Cycle 1 Day 1 and Cycle 1 Day 8 (after a minimum fast of 6 hours) by site staff after the collection of the biomarker samples and pre-dose PK sample. Subjects are allowed to eat after PK Sample #4 (Hour 2) has been collected. On Cycle 1 Day 15, the morning dose of LAM-002A should be orally administered (after a minimum fast of 6 hours) by site staff immediately after collection of the pre-dose PK and biomarker samples.

For subjects receiving the intermittent LAM-002A regimen, prophylactic antiemetics are a required component of the regimen as described in Section 6.8.2.6.2. After initiation of the antiemetic regimen, the morning dose of LAM-002A should be orally administered on Cycle 1 Day 1 and Cycle 1 Day 10 (after a minimum fast of 6 hours) by site staff after the collection of the biomarker samples and pre-dose PK sample. Subjects are allowed to eat after PK Sample #4 (Hour 2) has been collected. Similarly, on Cycle 1 Day 8 and Cycle 1 Day 15, the antiemetic regimen should be initiated and the morning dose of LAM-002A should be orally administered (after a minimum fast of 6 hours) by site staff immediately after collection of the pre-dose samples.

When given as a component of combination therapy with rituximab, LAM-002A will be started on Cycle 1 Day 1 with a BID schedule. LAM-002A will be administered after administration of premedications (see Section 6.8.3.1) and ~15 to 30 minutes prior to the start of the initial

rituximab infusion. On Cycle 1 Day 8, the morning dose of LAM-002A will be administered after premedications (see Section 6.8.3.1) and ~15 to 30 minutes prior to the rituximab infusion/injection.

When given as a component of combination therapy with atezolizumab, LAM-002A will be started on Cycle 1 Day 1 with a BID schedule. LAM-002A will be administered ~15 to 30 minutes prior to the start of the initial atezolizumab infusion. On Cycle 1 Day 8, the morning dose of LAM-002A will be administered in the clinic.

6.8.2.3. LAM-002A Self-Administration

Except for the days where treatment is administered in the clinic, LAM-002A will be self-administered orally, BID or TID of each 28-day cycle until disease progression or other discontinuation criteria are met. When taking the drug at home, subjects should be advised to take LAM-002A with \geq 4 oz. (\sim 160 mL) of water at the same times each day. Subjects on a BID schedule will be advised to take the doses at \sim 12 hours apart (e.g., 8:00 AM and 8:00 PM) (+/-1-hour window). Subjects on a TID schedule will be advised to take the doses at intervals of \sim 6 to 8 hours. When self-administering LAM-002A at home, subjects may take the drug in the fed or fasted state. On PK days, subjects should come to clinic fasted (a minimum fasting state of 6 to 8 hours) and take the dose at the site under supervision. All subjects will be required to complete a dosing diary, which must be returned to the site for review at each site visit.

For those subjects taking LAM-002A with continuous administration, the drug should be taken according the prescribed BID or TID schedule without interruption unless toxicity or intercurrent illness requires a modification to the dosing regimen (see Section 6.8.2.5).

For those subjects taking LAM-002A with intermittent administration, the drug should be taken in repeated 7-day sequences comprising BID self-administration for 3 days (6 doses) followed by 4 days without dosing. If the cadence of the on-off periods is interrupted due to toxicity, intercurrent illness, or other reasons, the medical monitor should be consulted regarding the timing of therapy resumption and dose modification (see Section 6.8.2.5).

6.8.2.4. LAM-002A Dose Schedule Interruptions and Vomited Doses

Subjects on a BID schedule who have a delay in administration of a dose of LAM-002A of < 6 hours should take the planned dose as soon as possible after the intended time of administration. For subjects who have a delay in administration of LAM-002A of ≥ 6 hours, the dose should not be taken. The planned timing of subsequent LAM-002A dosing should not be altered.

Subjects on a TID schedule who inadvertently have a delay in administration of a dose LAM-002A of ≤ 1 hour, the planned dose should be taken with no changes to the subsequent dose schedule. For subjects who have a delay of > 1 hour but ≤ 4 hours, the planned dose should be taken; however, all future doses for that day should be shifted later by a corresponding amount. It is recommended that subjects take the last dose of study medication no later than 12:00 midnight on any study treatment day. For example, if the 7:00 AM dose is taken at 10:00 AM, the next dose should be taken ≥ 6 hours later (after 5:00 PM), and the last dose should be taken ≥ 6 hours thereafter (between 11:00 PM and 12:00 midnight). For subjects on a TID schedule who have a delay in administration of LAM-002A of > 4 hours, the dose should

not be taken. LAM-002A administration may continue but the missed dose should not be made up and the planned timing of subsequent LAM-002A dosing should not be altered.

For subjects who vomit shortly after taking LAM-002A, the vomited dose should not be replaced. The planned timing of subsequent LAM-002A dosing should not be altered.

6.8.2.5. LAM-002A Dose Modifications

The AEs associated with LAM-002A administration have included gastrointestinal toxicities of nausea, vomiting, and diarrhea, typically beginning shortly after initiation of drug administration.

If a subject experiences an AE that is suspected to be related to LAM-002A, appropriate supportive care (e.g., antiemetics, antidiarrheals, therapy for tumor lysis syndrome [TLS]) should be instituted consistent with the nature of the event.

If a subject experiences an LAM-002A-related DLT (reference Table 4) or other AE requiring a dose modification, then the LAM-002A administration should be interrupted until the toxicity recovers to Grade ≤ 1 or baseline. Upon resumption of LAM-002A, the total daily dose of LAM-002A should be reduced using an appropriate dose level or schedule (reference Table 3) as agreed between the investigator and medical monitor. Successive adjustments to progressively lower total daily dose levels can be made. If the subject cannot tolerate LAM-002A after a decrease to Dose Level -1 (25 mg BID), then the subject should be discontinued from LAM-002A therapy unless continued treatment is permitted by the medical monitor.

After the LAM-002A dose is reduced, the dose can be maintained at that dose level or schedule, even if there is minimal or no toxicity with the reduced dosing regimen. However, if the subject tolerates a reduced total daily dose of LAM-002A for \geq 4 weeks then the LAM-002A dosing regimen may be reescalated to a higher total daily dose level at the discretion of the investigator and with the concurrence of the medical monitor. Such reescalation may be particularly warranted if the AE comprised TLS or if further evaluation reveals that the AE that led to the dose reduction was not related to LAM-002A. Successive adjustments to progressively higher total daily dose levels can be made. However, the escalated dose cannot exceed the total daily starting dose level for that subject during the first 2 cycles of therapy.

Individual subjects who initiated treatment at a total daily dose level at or below the lower of the currently established MTD or the RP2D and who have not experienced a DLT after ≥ 2 cycles of treatment may have the LAM-002A total daily dose escalated to the next higher dose level if both the principal investigator and the medical monitor agree that a dose escalation is medically warranted (e.g., for a subject with stable disease who is tolerating the current dose level of LAM-002A therapy). In such subjects, successive adjustments to progressively higher total daily dose levels can be made at intervals of ≥ 4 weeks with the condition that the escalated total daily dose level cannot exceed a LAM-002A dose of 150 mg BID when administered continuously or the lower of the currently established MTD or RP2D of LAM-002A when given intermittently.

In a subject who experiences a DLT precluding resumption of LAM-002A therapy during a cycle, a new cycle of treatment may begin at the later of Day 29 or when AEs or laboratory abnormalities related to LAM-002A have returned to baseline levels. If drug-related AEs or laboratory abnormalities precluding further administration of study drug are not resolved to

baseline by Day 29, week-by-week delays in initiating the new cycle of treatment should be instituted. When all drug-related AEs and laboratory abnormalities have returned to baseline, the next cycle of therapy can be initiated. Upon initiation of a new cycle of therapy, the prior cycle of therapy will be considered completed.

Investigators are to discuss modifications in the dosing regimen with the medical monitor. The appropriate clinic staff should dispense the LAM-002A for the new dose level or schedule and instruct the subject/caregiver about the change in the dosing regimen.

6.8.2.6. LAM-002A Supportive Care

6.8.2.6.1. Antiemetics for Subjects Taking LAM-002A by Continuous Administration

For subjects taking LAM-002A via continuous administration, sites should consider providing study participants with antiemetics and antidiarrheals so that these supportive care medications are readily available in case gastrointestinal symptoms related to LAM-002A develop.

For subjects taking LAM-002A via continuous administration, it is recommended that, if prophylactic or therapeutic antiemetics are required, subjects be offered 2 mg of the serotonin antagonist, granisetron (Kytril®, Granisol®), as an oral tablet or solution every 6 hours as needed. If subjects have persistent nausea or vomiting, consideration can be given to a 10-mg subcutaneous injection of the extended release form of granisetron (Sustol®). Alternatively, application of a 31.3 mg granisetron transdermal patch (Sancuso®) every 3 to 7 days can be offered. For transdermal prophylaxis, 24 to 48 hours may be necessary to allow a sufficient period to achieve effective granisetron systemic concentrations. Use of the serotonin antagonists, ondansetron (Zofran®, Zuplenz®) or dolasetron (Anzemet®), is discouraged due to the possibility that such agents could prolong the cardiac QT interval.

The dopamine antagonist, olanzapine (Zyprexa®), at doses of 2.5 to 10 mg, may be considered alone or in conjunction with serotonin antagonists or other types of antiemetic agents. Olanzapine doses of 10 mg may be sedating, which could be helpful for certain subjects, but may represent a concern for others, particularly for those who are elderly.

Based on currently available information regarding LAM-002A metabolism, the neurokinin 1 receptor antagonist, rolapitant (Varubi®), can be considered, but aprepitant (Emend®) or netupitant+palonosetron (Akynzeo®) should be avoided because these drugs may inhibit CYP3A4 and/or CYP2C9 activity.

Other classes of antiemetic medications that may be employed include dopamine antagonists or benzodiazepines if such drugs do not pose risks of QT prolongation or drug-drug interactions. Given the possibility that LAM-002A may alter immunological mechanisms, use of systemic corticosteroids (e.g., dexamethasone) should be minimized (particularly when coadministered with atezolizumab) to avoid immunocompromise; however, corticosteroids can be introduced if other types of antiemetic agents are not sufficiently effective.

6.8.2.6.2. Antiemetics for Subjects Taking LAM-002A by Intermittent Administration

Because LAM-002A induces dose-dependent nausea and vomiting, subjects who are taking LAM-002A by intermittent administration are required to receive antiemetic supportive care.

Version 9, 18 Feb 2020

The following prophylaxis regimen should be started ≥30 minutes before initiation of each LAM-002A 3-day treatment sequence:

- Dexamethasone 12 mg PO on Day 1 and then 8 mg PO on Day 2 and Day 3
- Granisetron 2 mg PO on Day 1 and then 1 mg PO BID on Days 2 and 3
- Olanzapine, 10 mg PO on Day 1 and then 10 mg PO on Days 2 and 3

The study subject must be sent home from the clinic with sufficient dexamethasone, granisetron, and olanzapine to ensure that the supportive care medications are readily available to the subject for each of the four 3-day courses of LAM-002A therapy during each 28-day cycle.

Doses of dexamethasone and olanzapine may be adjusted to tolerance. Other antiemetic drugs (eg, neurokinin 1 receptor antagonists, dopamine antagonists, or benzodiazepines) may be considered in consultation with the medical monitor.

